5.1.2 Participant Exclusion criteria

1. Did the patient present to the hospital more than 48 hours post injury?
2. Has the patient received more than 2 doses of LMWH or Aspirin for initial prophylaxis?

The PREVENT CLOT study protocol is the confidential intellectual property of the PREVENT CLOT Principal Investigators, Steering Committee, and the University of Maryland Baltimore and METRC and cannot be used in any form without the expressed permission of the Principal Investigators.

3. Is the patient on long term blood thinners (other than low-dose aspirin or platelet inhibitors such as Plavix or Aggrenox)?
4. Did the patient have a VTE within the last 6 months?
5. Is the patient on therapeutic (as opposed to prophylactic) blood thinners for an acute issue at the time of admission?
6. Does the patient have a newly diagnosed indication for therapeutic blood thinners (for example vascular injury) that will require therapeutic anticoagulation for more than one week?
7. Does the patient have an allergy to aspirin, or NSAIDs, or a history of heparin induced thrombocytopenia, or other medical contraindication to blood thinners (e.g. peptic ulceration, gastrointestinal bleeding, etc)?
8. Is the patient on higher dose aspirin (>81 mg once a day or higher) for medical reasons or will be treated with higher dose aspirin?
9. Does the patient have underlying chronic clotting disorders (i.e. Factor V Leiden, hemophilia, Protein C and S deficiency) that require full dose anticoagulation or are a contraindication to VTE chemoprophylaxis?
10. Does the patient have end stage renal disease, or impaired creatinine clearance <30 ml/min at time of randomization?
11. Is the patient pregnant or lactating?
12. Does the patient speak neither English nor Spanish?
13. Is the patient is a prisoner?
14. Is the patient is likely to have severe problems maintaining follow-up?
15. Is the patient, based upon the clinical judgment of the treating clinician, NOT equally suited for treatment with either Aspirin or Lovenox?
16. Should the patient be excluded for other reasons at the discretion of the treating physician?
17. Does the patient have a known COVID-19 diagnosis prior to fracture treatment or within 3 months of the index fracture?

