Due to the acute nature of injuries experienced by the trauma patient population, some patients may have conditions or treatment plans that are unknown at the time of enrollment that, but when discovered later causes them to become ineligible. Patients who are enrolled and later meet an exclusion criterion that was present but undiagnosed at the time of enrollment will be withdrawn and considered a late ineligible participant.

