3. the number of patients not enrolled and associated reasons
4. the number of enrolled and randomized patients
5. number randomized to aspirin group, number randomized to low-molecular-weight heparin (LMWH) group
6. within treatment group, the number of late ineligibles, late refusals, and inappropriate enrollments
7. within treatment group, the number initiating treatment protocol
8. within treatment group, information on 90 day follow-up (including separate metrics for key endpoints)
9. within treatment group, the number included in the per-protocol analysis

The independent adjudication committee will make the final determination on late ineligibles and inappropriate enrollments while masked to the treatment arm. Late ineligibles and inappropriate enrollments will be removed from all analyses. The outcomes, complications, adverse events of late ineligibles and inappropriate enrollments who received treatment will be reported, to the extent possible.

3 Follow-up Time

Patients were expected to return for a study follow-up visit at 90 days post admission. If participants are unable to return to the clinic, they may be contacted to complete the 90 days follow up visit via phone or email. In addition, medical record reviews will be conducted to determine whether there was documented clinical/research contact beyond the last study follow-up visit. If that visit occurred less than 90 days following randomization, the end of follow up will be defined as the last study follow-up visit or the last clinical/research contact if applicable, and follow-up time will be the duration between randomization and the end of follow up. A figure showing the distribution of follow-up time through 90 days by treatment group will be produced. Differences between treatment groups based on follow-up time through 90 days will be evaluated. Details of reasons for premature study discontinuation will be presented.

4 Baseline Characteristics

A table will report summary statistics of baseline characteristics of participants by treatment groups. Characteristics will include age, sex, body mass index, tobacco use, history of venous thromboembolism, co-morbidities, additional medications, health insurance status, injury severity score, and injury region.

5 Adherence to Treatment Protocol

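### The late-ineligible rule has no test to separate a pre-existing condition from an early clot or bleed, so an outcome event can lead to removal of the patient who had it from every analysis

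*Combined protocol and SAP*

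**What the plan says.** All protocol references are to version 11.0 unless stated.

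**The rule.** The closing paragraph of protocol 5.1.2 starts from the fact that "some patients may have conditions or treatment plans that are unknown at the time of enrollment". It then provides that enrolled patients who "later meet an exclusion criterion that was present but undiagnosed at the time of enrollment will be withdrawn and considered a late ineligible participant".

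**The criteria it can draw on (5.1.2).** Criterion 4 asks: "Did the patient have a VTE within the last 6 months". Part of criterion 7 is "other medical contraindication to blood thinners (e.g. peptic ulceration, gastrointestinal bleeding, etc". Criterion 6 is a "newly diagnosed indication for therapeutic blood thinners (for example vascular injury) that will require therapeutic anticoagulation for more than one week". Criterion 9 covers chronic clotting disorders, but only those that need full-dose anticoagulation or rule out chemoprophylaxis.

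**Who decides, and what follows.** SAP section 2 says: "The independent adjudication committee will make the final determination on late ineligibles and inappropriate enrollments while masked to the treatment arm". It then removes both groups from all analyses, counts them by arm in the CONSORT diagram, and reports the outcomes of those who were treated as far as that can be done. Protocol 8.8 replaces withdrawn patients. Protocol 10.1 allows up to 12,400 randomized so that 12,200 can be analysed.

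**The outcomes.** Protocol 3.3.2 counts PE at any level and DVT confirmed by imaging. Protocol 3.3.3 counts bleeding that meets a composite definition. SAP section 1 starts the clock at randomization.

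**The concern.** Removing a patient after randomization is harmless to the comparison when the reason is a fact fixed before randomization and found in a way unrelated to outcome. Here the discovery can be the outcome itself. A patient imaged for leg swelling in the first days after enrollment may be found to have a clot. A patient with the same silent clot and no symptoms is never imaged and stays in. The first can be classed as a trial event or as a patient who should not have been enrolled, and the plan does not say which.

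At stake are the PE, DVT and bleeding estimands (SAP 7.3.3 and 7.3.4). If one arm has more early events, it can lose more of them, and the observed difference shrinks. The primary estimand is exposed to a lesser degree: death is not an exclusion criterion, but a removed patient who later dies takes that death out of the count.

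**Working it through.** **1. Can one event be read both ways?**

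- *Early VTE.* It meets the outcome definition in 3.3.2, which says nothing on onset. It also meets criterion 4 if someone judges that it predates enrollment. Section 6.2.2 adds no clinical assessment, so no study imaging shows that a clot was absent at baseline. One example in SAP section 1 has study drug starting three days after randomization.
- *GI bleed or ulcer.* A bleed that meets the 3.3.3 composite is an outcome. The bleed, or an ulcer found while investigating it, also fits criterion 7.
- *Criteria 6 and 9.* These are reached only indirectly. A treated clot fits criterion 6 as worded, and a clotting disorder may surface in a work-up after a clot. Both links are inference; the document's own example for criterion 6 is vascular injury.
- *Masking.* SAP section 2 masks the committee to arm. Nothing masks it to the event, and nothing says how cases reach it in a trial that is not blinded (10.2).

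**2. The plan's own figures reproduce.** Inputs: 6,100 per arm, 1% mortality, margin 0.75 points (10.1); two-sided 96.2% interval, so z = 2.075 (SAP 7.4).

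- SE = sqrt(2 × 0.01 × 0.99 / 6,100) = 0.180 points. Power = Φ(0.75/0.180 − 2.075) = 98.2%. With 7.5% loss (5,642 per arm) it is 97.3%.
- Simulation (400,000 runs, looks at one third, two thirds and the end with 99.6%, 98.8% and 96.2% intervals) gives 97.1% and 96.2%, with false non-inferiority of about 2.0-2.1% at 1% versus 1.75%. This agrees with the stated more than 95% and less than 2.5%.

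**3. Illustration for mortality.** Assumption: *k* deaths are removed from the aspirin arm only, when the true risks are 1% and 1.75%. The documents give no such split. Shift = k/6,100. With 106.75 expected aspirin deaths, the aspirin risk becomes (106.75 − k)/(6,100 − k). The simulation applies the removal at the final analysis.

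| k | Shift (points) | False non-inferiority, formula | Simulation |
|---|---|---|---|
| 0 | 0 | 1.9% | 2.0% |
| 1 | 0.016 | 2.3% | 2.5% |
| 2 | 0.033 | 2.7% | 3.0% |
| 5 | 0.082 | 4.6% | 5.0% |
| 10 | 0.164 | 9.9% | 10.2% |

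A milder assumption removes the same *fraction* of deaths from both arms, which still takes more from the arm with more deaths. By formula, 2%, 5% and 10% give 2.3%, 2.9% and 4.5%.

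**4. Illustration for VTE.** Version 11.0 gives no VTE rate. Version 1.0, section 10.1, assumed 1.5% for PE on LMWH; taking that for the aspirin arm gives 0.015 × 6,100 = 91.5 events. Removing 5%, 10% or 20% of them from that arm only shifts the difference by 0.08, 0.15 or 0.30 points, against a 95% half-width of 0.43. At an assumed 3%, the shifts are 0.15, 0.30 and 0.60 points against 0.61.

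**5. Are removals needed for power?** No. Analysing all 12,400 (6,200 per arm) gives 98.3%, or 97.5% with 7.5% loss.

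**The case against.** **The rule requires the criterion to have been present at enrollment.** This is correct. A reader might infer that any clot or bleed after randomization makes a patient ineligible, or that criteria 4, 6, 7 and 9 are all trial outcomes. The text supports neither. A new event does not qualify, and only criterion 4 and the bleeding part of criterion 7 overlap directly with outcomes. What stands is that the judgement of presence has no test behind it.

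**In-trial events already have a route.** Section 6.2.1 records VTE and PE as complications, Appendix B records therapeutic anticoagulation with its reason, and 7.3 keeps patients in follow-up when the assigned drug is no longer appropriate. This shows the intent, but it does not say which provision governs when 5.1.2 also applies.

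**Removals will be visible.** CONSORT counts by arm and separate outcome reporting help, and they weaken any claim that events would vanish. The reporting is limited to treated patients and to what is feasible, and it does not put these patients back into the estimands.

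**The mortality figures are a worst case.** This is fair. At the superseded PE-death planning rate of 0.25%, about 15 such deaths are expected per arm, so ten one-sided removals would be about two thirds of them. With 61 LMWH deaths, the upper bound is 0.749 points at 82 aspirin deaths and 0.766 at 83, and a reader might take that as evidence of fragility; it is the knife-edge of any fixed margin. The 200-patient allowance covers inappropriate enrollments too, across 17 criteria, so setting it beside the 122 expected deaths shows no overlap.

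**The direction is not established.** This stands. Hypothesis 3 expects more bleeding on LMWH; removing bleed-related LMWH deaths would push the result away from non-inferiority. For PE and DVT, 10.5.1 and SAP 7.4 give intervals without tests or a margin, so the risk is a biased estimate rather than a flipped test.

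**It is only the intention-to-treat issue again.** They overlap, since harm needs the removal. The added point is that selection here can depend on outcome.

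**Conclusion.** The concern holds in a limited form, and the rule should be changed. The late-ineligible rule, joined with removal from all analyses, does not separate pre-existing conditions from outcome events, and masking to arm does not prevent selection on events. The exposure falls mainly on the secondary PE, DVT and bleeding estimands and reaches mortality only through removed patients who die.

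The size is unknown because the documents give no count, split or timing of such removals. The illustration rests on one-sided removal at 1% versus 1.75%. On that assumption two aspirin deaths are enough to exceed the stated 2.5%, and one is not. Equal numbers of removed deaths in the two arms would leave the mortality difference almost unchanged.

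**What to change.** 1. In protocol 5.1.2 and SAP section 2, state that a patient is late ineligible only if the criterion is shown to have existed before randomization by evidence that did not arise from a trial outcome event. An injury present at admission but imaged later for an unrelated reason would still qualify; restricting the committee to records dated before randomization would be too strict.
2. State that a VTE or bleed diagnosed after randomization, or a condition found because of one, never makes a patient late ineligible for analysis. The patient stays in follow-up and in the analysis.
3. Have the committee decide masked to outcome events as well as to arm.
4. Add a sensitivity analysis of all randomized patients.
5. Reconcile 5.1.2 with 7.3 (continued follow-up when the assigned drug is no longer appropriate) and with the intention-to-treat statement in 10.5.1.

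The cost is one protocol paragraph, a short SAP addition, a committee instruction and one extra analysis. A few patients with truly pre-existing clots will stay in, balanced between arms by randomization. Power is not reduced.

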5.1.3 Co-Enrollment Guidelines

The PREVENT CLOT study protocol is the confidential intellectual property of the PREVENT CLOT Principal Investigators, Steering Committee, and the University of Maryland Baltimore and METRC and cannot be used in any form without the expressed permission of the Principal Investigators.

Patients may be co-enrolled into this and other studies, depending on the practices of the local IRB. Co-enrollment must be documented, and event reporting for either study must be reported for both projects.

6. STUDY PROCEDURES

6.1 Screening and Enrollment

6.1.1 Screening

All patients 18 years of age and older with an orthopaedic injury and for whom prophylactic clot prevention medication is indicated will be screened for eligibility at each site by the local Research Coordinator in close collaboration with the surgeon investigators. In this study, it will be important to enroll patients soon after admission to ensure study medication can commence in a timely manner.

Screening will take place either in the hospital or remotely by a Research Coordinator depending on access available to hospital facilities. Remote screening will involve communication between Advanced Practice Providers and a member of the study team in order to document all eligible patients even when the Research Coordinator is not physically at the site. Patients screening status will be logged using REDCap website and either randomized, when eligible, or excluded as an ineligible patient.

A partial HIPAA Waiver will be requested for the purposes of screening for enrollment. The study team will discuss all participants meeting inclusion criteria, and complete and submit a screening case report form (CRF) on every potentially eligible participant. The medical record will be reviewed to assess for exclusion criteria, and the results will be entered into REDCap, the METRC electronic data capture system, in order to document screen failures. The study PI will be available via text or email to answer questions regarding study eligibility. This service will be active during regular east and west coast business hours. When the study PI is not available, this coverage will be provided by a designated co-investigator. Contact information for the PI and alternate contact is available in Appendix A.

6.1.2 Consent and Enrollment

In-person consent:

Once eligibility has been confirmed, the informed consent process will be completed by the Research Coordinator and/or a clinician certified to participate in this study. Eligible study participants or their legally authorized representative (LAR) will be approached as soon as they are able to give consent, and may be enrolled in the study through the time that the first two doses of anticoagulation therapy are administered; i.e. they may receive 2 doses of SOC (as defined by the center) therapy prior to randomization and initiation of the study-directed medication. Individual sites will develop local procedures that will ensure these requirements can be met. Patients and their families may be provided with a pamphlet (Attachment C) describing

The PREVENT CLOT study protocol is the confidential intellectual property of the PREVENT CLOT Principal Investigators, Steering Committee, and the University of Maryland Baltimore and METRC and cannot be used in any form without the expressed permission of the Principal Investigators.

the study, the risks and benefits of participation and what will be expected of them if they choose to participate. A video (Attachment D) describing the study treatment and procedures may be provided to assist with the recruitment process. If a patient is unable to consent before 2 doses of SOC anticoagulation therapy are administered and there is no LAR available, the patient will not be eligible for study participation and will be recorded as such. Consent will be obtained in accordance with principles of GCP and ICH guidelines.

Tele or remote consent:

When the Research Coordinator is unable to access the site tele or remote consenting process will be completed by the Research Coordinator in collaboration with an Advanced Practice Provider. Once eligibility is confirmed, the Advance Practice Provider will approach the participant or LAR to provide information on the study, a physical copy of the consent form and an opportunity to be contacted by phone or video call from the Research Coordinator. Once notified, Research Coordinator will contact all willing participants or their LAR and provide additional information about the study and also offer to send a link to the patient recruitment video (Attachment D) for the participant/LAR to view on a personal device. The Research Coordinator will offer to answer questions or put the participant in contact with the treating Physician when necessary. The participant will be offered the opportunity to consult with any family members or friends prior to making a decision on consenting into the study. Consent will be obtained over the phone or video call and documented by the Research Coordinator.

Remote review of consent will not change the requirement for written consent to be documented, unless local regulations relax those requirements for the duration of the COVID-19 pandemic response.

A prototype consent has been prepared for this study (Attachment A) and individual sites may add material but may not delete material thought to be necessary for informed consent. Clinical sites may reformat and reword information to conform to their local requirements. The consent form describes the purpose of the study, the procedures to be followed, and the risks and benefits of participation. Copies of the signed consent forms will be given to the patient, and this fact will be documented in the patient's record. Once the patient is enrolled into the study they may receive a card/key chain (Attachment E) for study identification and to prompt adherence to the study assigned treatment.

All study materials will be provided in English and/or Spanish as appropriate.

Following completion of informed consent, the participant information will be entered into REDCap where a study number will be assigned, final eligibility criteria confirmed, and the participant will be randomized to a treatment group.

6.1.3 Assessing Capacity to Consent and Consenting a Proxy Respondent

The PREVENT CLOT study protocol is the confidential intellectual property of the PREVENT CLOT Principal Investigators, Steering Committee, and the University of Maryland Baltimore and METRC and cannot be used in any form without the expressed permission of the Principal Investigators.

The research staff will endeavor to answer all questions posed by the patient and his/her family to ensure their understanding of the protocol. After introducing the study and reviewing the consent form, the research coordinator will pose several questions assessing the participant's comprehension of the study and what it means to participate, their appreciation of the consequences of participation, and their ability to consider alternatives to participation. The Research Coordinator will ask the questions and determine the appropriateness of the responses. If the Research Coordinator is at all unsure about the patient's ability to consent s/he will consult with the study site PI.

By virtue of the types of injuries studied (resulting from high energy mechanisms such as high speed motor vehicle crashes, high falls, and blast injuries) it is expected that we will have patients with an associated traumatic brain injury which may render them unable to provide consent for the study. Other patients may remain intubated for some time due to lung issues or other reasons related to their trauma. It will be important not to exclude these patients from the study, as it would significantly reduce our ability to produce generalizable knowledge. These patients are at no greater risk of adverse consequences by virtue of their participation in the study, and should be given the same opportunity to participate.

A legally authorized representative (LAR) with reasonable knowledge of the potential participant will be approached to consent on the patient's behalf if one of the following is true:

- The patient is unresponsive or intubated (and likely to remain unresponsive or intubated during the enrollment window for the study).
- The patient cannot adequately answer at least 2 questions regarding study participation or it is determined that the patient's level of cognition is not likely to change before study medication can be initiated.

The choice of LAR will follow standard procedures and be any of the following: Legal guardian, Proxy (health care agent) named in an advance directive or durable power of attorney for health care; or Family member or other surrogate identified by the state law on health care decisions.

Guidance will be provided to assist the LAR in making the consent decision. They will be advised to base the decision on the participant's expressed wishes, or, if these are not known, what they believe the participant would have desired under the circumstances of the injury, their beliefs and values and a willingness to administer the study medication, if the patient is still unable to consent at the time of discharge. If the LAR does not know what the participant would have wanted, the LAR will be advised to base the decision with the participant's best interest in mind. They will be asked to carefully consider how much leeway the participant would likely give the LAR in making the choice about participation in the study.

Recognizing that consent is an ongoing process, the study team will continue to assess the participant for their ability to provide consent, and at the earliest possible time, will obtain informed consent from the patient him or herself. Similarly, any participant may withdraw consent at any time during participation in this study.

The PREVENT CLOT study protocol is the confidential intellectual property of the PREVENT CLOT Principal Investigators, Steering Committee, and the University of Maryland Baltimore and METRC and cannot be used in any form without the expressed permission of the Principal Investigators.

